Version 8 adds a blood draw at 36 months (Study Day 1095), 48 months (Study Day 1460), and 60 months (Study Day 1825) for immunological assays, as well as a bone marrow aspiration procedure at 60 months (Study Day 1825) for immunological assays and associated safety visit and follow-up phone call. The rationale for these additional visits/specimen collections are 1. To assess the half-life/decay kinetics/durability of HPV-specific antibody responses in blood following vaccination and 2. To assess the half-life/decay kinetics/durability of HPV-specific plasma responses in the bone marrow following vaccination. We do not anticipate that a second bone marrow aspirate will incur any additional risks to participants on basis that participants in other tissue sampling studies at Hope Clinic that have had more than one bone marrow aspiration procedure with no complications to date. Version 8 also adds an anonymous survey by email or text about the bone marrow aspiration procedure at the time of the two follow-up phone calls and minor changes to language for consistency.

Version 7 changes compensation of bone marrow aspiration from \$200 to \$350 and adds Hope Clinic as a site for bone marrow aspiration, as well as lorazepam, an anxiolytic, as a study medication that may be administered sublingually per manufacturer dosing recommendations prior to the bone marrow aspirate procedure per the clinician performing the procedure. It also corrects some information about the immunological screening assay and laboratory conducting that assay; makes consistent the time to notify ISM of SAEs (and IRB if study related) as 24 hours; and changes the lidocaine dosage for bone marrow aspiration from 2% to 1-2% to be consistent with other tissue sampling protocols at Hope Clinic.

Version 6 changes the study enrollment number to 50. The eligibility based on age has been changed to 18 – 45 instead of > 18 – 45. Visit window days have been updated as follows: Day 61 to Visit 8 +1 day; Day 67 to Visit 8 + 7 ±1 days; Day 74 to Visit 8 + 14 ±5 days; Day 90 to Visit 8 + 30 ±5 days; Day 187 to Visit 13 + 7 ±1 day; Day 194 to Visit 13 + 14 ±5 days; Day 210 to Visit 13 + 30 ±5 days. Study of procedures table has been edited to reflect the aforementioned changes.

Version 5 changes visit window timelines to expand the Visit 2 window from Day -30 to Day 0 (currently Day -30 +/-1) and makes minor changes to visits included for endpoint analyses for consistency throughout protocol

Protocol Title: Assessing immunological basis of durable antibody responses to 9-valent HPV vaccination

Version 4 changes requirements for Visit 4 and Visit 9, which are now optional. Windows for Visit 8 and Visit 13 have been extended to +/- 5 days. Visit windows for FNA in Group 1, Group 2, and Group 3 have been extended to +/- 5 days. Baseline FNA for Group 2 has been moved to before dose 2 and for Group 3 to before dose 3. The version number, date, and version history were updated.

Version 3 removes blood chemistry and blood count values from inclusion criteria, modifies interpretation of vital signs and safety labs, adds optional finger prick blood collection by microsampler at five visits, and makes minor changes to follow up visit days and saliva sampling visit days for consistency throughout protocol. The version number, date, and version history were updated. The table of contents formatting was updated. Grammatical and formatting changes were updated throughout the document.

Version 2 was updated to add HIPAA Compliant Emory RedCap database and HIPAA compliant clinical management database - Clinical Conductor. The version number and date were updated throughout the document; 2021 November 30. The table of contents formatting was updated. Grammatical and formatting changes were updated throughout the document.

Table of Contents

1. Study Summary	4
2. Objectives.....	6
3. Background	7
4. Study Endpoints	9
5. Study Intervention/Investigational Agent.....	10
6. Procedures Involved.....	12
7. Data and Specimen Banking.....	19
8. Sharing of Results with Participants.....	19
9. Study Timelines	20
10. Inclusion and Exclusion Criteria.....	20
11. Local Number of Participants	23
12. Recruitment Methods	23
13. Withdrawal of Participants.....	23
14. Risks to Participants	24
15. Potential Benefits to Participants.....	28
16. Compensation to Participants.....	28
17. Data Management and Confidentiality	28
18. Provisions to Monitor the Data to Ensure the Safety of Participants	30
19. Provisions to Protect the Privacy Interests of Participants	40
20. Economic Burden to Participants	40
21. Consent Process	40
22. Setting	41
23. Resources Available.....	42
24. Multi-Site Research when Emory is the Lead Site	43
25. References.....	43
26. Appendices	46

1. Study Summary

Study Title	Assessing immunological basis of protection by and durable antibody responses to 9-valent HPV vaccination
Study Design	
Single center, longitudinal cohort study in which participants will receive 9-valent HPV vaccine according to package insert (i.e., one dose of 9-valent HPV vaccine on D0 followed by a second dose 2 months later and a third dose 6 months later).
 
Immune responses in the blood, saliva, bone marrow, and lymph nodes will be assessed in participants receiving the HPV vaccine.
 
Blood samples for immunologic testing will be collected at screening (from D-60 to D-45), on D0 (before vaccination), D1 (optional visit), D7, D14, D30, D60 (before vaccination), Visit 8 + 1 day (optional visit), Visit 8 + 7±1 days, Visit 8 + 14±5 days, Visit 8 + 30±5 days, D180 (before vaccination), Visit 13 + 7±1 days, Visit 13 + 14±5 days, Visit 13 + 30±5 days, D365, D730, D1095, D1460, and D1825. Saliva samples for antibody testing will be collected on D0 (before vaccination), D30, D60 (before vaccination), Visit 8 + 30±5 days, D180 (before vaccination), Visit 13 + 30±5 days, D365, and D730.
 
Axillary lymph node sampling by fine needle aspiration will be done 3 times per group. Group 1 will have lymph node sampling done D-30 to D0, D14, and D30. Group 2 will have lymph node sampling done D60, Visit 8 + 14±5 days and Visit 8 + 30±5 days. Group 3 will have lymph node sampling D180, Visit 13 + 14±5 days, and Visit 13 + 30±5 days. Bone marrow sampling will be done for all groups at D730 and D1825.

Primary Objective	
• Determine number of participants with a minimum four-fold rise in post-vaccination HPV-16 and HPV-18 neutralizing antibody titers

Protocol Title: Assessing immunological basis of durable antibody responses to 9-valent HPV vaccination

Secondary Objective	
1. Assess magnitude and durability of HPV specific Bmem responses at baseline and following 9-valent HPV vaccination
Exploratory Objectives	
1. Determine if 9-valent HPV vaccination induces germinal center formation in humans by assessing the generation of germinal center T follicular cell (GCTfh) and germinal center B cell (GCB) responses in lymph nodes2. Test whether the magnitude or quality of GCTfh responses correlates with the durability of antibody and B cell responses induced by 9-valent HPV vaccination3. Assess correlations between the phenotype of GCB and the magnitude, type, and durability of B cell memory induced by 9-valent HPV vaccination.4. Compare B cell antibody repertoires and gene expression (RNA sequencing) profiles of HPV-specific memory B cells (Bmem), plasmablasts (PB), GCB, and plasma cells (PC) following 9-valent HPV vaccination5. Define gene expression changes in blood following HPV vaccination relative to baseline6. Examine the magnitude and kinetics of the PB response at baseline and following 9-valent HPV vaccination7. Characterize the magnitude, phenotype, and durability of HPV-specific PC following 9-valent HPV vaccination8. To compare the isotypes, magnitude, kinetics, durability of saliva Ab responses with those serum Ab responses at baseline and following 9-valent HPV vaccination9. Evaluate associations between the magnitude or quality of circulating T follicular helper cells (cTfh) and the magnitude of Ab and PB responses induced by 9-valent HPV vaccination.10. Characterize magnitude, type, and functions of CD4 T cells at baseline and following 9-valent HPV vaccination11. Map HPV L1 CD4 T cell epitopes12. Determine if vaccine-elicited antibody responses collected with a blood microsampler

Protocol Title: Assessing immunological basis of durable antibody responses to 9-valent HPV vaccination

	
correlate with antibody responses found in serum to demonstrate feasibility for surveillance programs
 
13. Measure isotypes, magnitude, kinetics, durability, and neutralizing potency of HPV-specific serum Ab responses at baseline and following 9-valent HPV vaccination
 
14. Map antibody epitopes (polyclonal antibodies in blood or monoclonal antibodies cloned from B cells)

Research Intervention(s)/Interactions	
 • 3 doses of 9-valent HPV vaccine (Gardasil 9) at D0, D60, and D180 • 1-2% lidocaine injections • Lorazepam
Study Population	Men and women aged 18-45 years
Sample Size	8 female and 8 male participants split into 3 groups (Group 1 = 8 participants, Group 2 = 4 participants; Group 3 = 4 participants; with equal numbers female and male participants per group)
Study Duration for individual participants	Approximately 1892 days (~63 months)
Study Specific Abbreviations/ Definitions	
HPV – human papillomavirus
 
GCTfh – germinal center T follicular helper cells
 
cTfh – circulating T follicular helper cell
 
Bmem – memory B cell
 
PC – plasma cell (bone marrow)
 
PB – plasmablast (circulating)

Funding Source (if any)	Departmental Funding

2. Objectives

Specific aims

1. Determine if 9-valent HPV vaccination induces germinal centers in humans. We hypothesize that the HPV vaccine generates germinal centers as these structures are important for the formation of Bmem and we have previously shown that the 4-valent HPV vaccine elicits Bmem^{1,2}.
2. To determine if the magnitude or quality of GCTfh responses correlates with the durability of Ab and B cell responses induced by 9-valent HPV vaccination. We hypothesize that the quality of GCTfh will be a better predictor of Ab durability than GCTfh magnitude.
3. To assess correlations between the phenotype of GCB and the magnitude, type, and durability of B cell memory induced by 9-valent HPV vaccination. We hypothesize that we will observe more PC precursors than Bmem precursors in the germinal center given

that HPV Bmem rapidly wane to near baseline levels, whereas antibody levels are high and stable (suggesting potent and durable PC responses).

4. To compare B cell Ab repertoires and gene expression profiles of HPV-specific Bmem, GCB, and PC following 9-valent HPV vaccination. Previous work in mice suggests that Bmem repertoires are less somatically mutated and harbor more breadth than PC repertoires, which is what we expect to observe in our comparison here. However, we have also found that human anti-HPV Abs require little somatic hypermutation to potently neutralize HPV and thus we may find that fewer differences between these repertoires in the case of HPV.
5. To define gene expression changes occurring post-vaccination in blood relative to baseline. Little is known about the gene expression changes that coincide with HPV vaccination, yet this information can advance our understanding of what innate and adaptive immune pathways are being activated by the HPV vaccine so that we can further investigate mechanism in vitro and in pre-clinical models.
6. To compare the isotypes, magnitude, kinetics, durability of saliva Ab responses with those serum Ab responses at baseline and following 9-valent HPV vaccination. Less is known about the composition, kinetics, and durability of mucosal anti-HPV Ab responses following vaccination compared to serum anti-HPV Ab responses. Although the isotypes and magnitude of the saliva Ab responses may differ with respect to serum Ab responses, we hypothesize that the kinetics and durability of saliva Ab responses will be similar to serum Ab responses, if saliva antibodies can be detected.
7. To determine if a microsampler can be used an alternative to venous blood collection for measuring antibody responses in blood for surveillance programs

3. Background

Human papillomaviruses (HPV) cause cervical, anal, oropharyngeal, vulvar, vaginal, and penile cancers. There are over 200 types of HPV³, of those, 12 are known to cause cancer and are considered carcinogens and high risk (HPV 16, 18, 31, 33, 35, 39, 45, 51, 52, 56, 58, and 59)⁴, though other types are capable of causing disease (e.g., genital warts)⁵. Currently, the 9-valent HPV vaccine is licensed and available in the U.S. It prevents infection by types that cause 90% of cancer cases (HPV 16, 18, 31, 33, 45, 52, and 58)⁶ and 90% of genital warts cases (HPV 6 and 11)⁷. The 9-valent vaccine was >96% effective at preventing high-grade cervical, vulvar, and vaginal disease in 16-26 year old women who did not have evidence of ongoing or prior infection (i.e., seronegative and PCR negative)^{8,9}, and the 4-valent HPV vaccine was >74% effective at preventing high-grade anal disease in 16-26 year old men without evidence of ongoing or prior infection¹⁰. Importantly, in persons aged 9-26 years at vaccination, the 4-valent (HPV 6, 11, 16, and 18) and 9-valent vaccines have shown to induce highly durable antibody responses for 10-14 and 7.5 years, respectively¹¹⁻¹⁴. Based on this data, mathematical modeling has predicted that antibody titers will remain above the antibody levels induced by natural infection for at least 15 years post-initial vaccine dose¹⁵. This is exceptional compared to many other approved and candidate subunit vaccines, whose antibodies drop to baseline more rapidly (e.g., influenza, acellular pertussis, tetanus,

Protocol Title: Assessing immunological basis of durable antibody responses to 9-valent HPV vaccination

hepatitis B virus, HIV-1 RV144 vaccine, herpes simplex virus 2 gB2 and gD2 vaccine)¹⁶⁻²¹. Moreover, in ~10% of persons who became seronegative for one of the HPV types by year 12, vaccine efficacy against cervical intraepithelial neoplasia grade 2 or worse remained at 100%, suggesting either a role for cellular memory or that antibodies at levels lower than those elicited by natural infection are protective¹¹. Moreover, Bmem elicited by a previous version of this vaccine (4-valent) have been shown to persist a minimum of 4.5 years post-vaccination²².

Most vaccines protect by generating antibodies. However, how this benchmark subunit vaccine – let alone any vaccine – elicits durable antibodies and Bmem is not understood. Is it dependent on antigen valency/avidity, given that the HPV vaccine antigen (L1) spontaneously assembles into virus like particles with 72 L1 subunits? Or is it due to trace amounts of DNA in the vaccine, which could provide B cell co-stimulation through pattern recognition receptors (e.g., TLR9) on B cells or other antigen-presenting cells (e.g., macrophages or dendritic cells)? Or does the vaccine induce and require GCTfh, which are critical to the formation of Bmem and long-lived PC? Further studies into how vaccines elicit potent, durable antibody responses will aid our ability to successfully and reliably design subunit vaccines that recapitulate these highly desired antibody responses.

Therefore, we designed this study to better understand how the 9-valent HPV vaccine elicits such potent and durable antibody responses in humans. We hypothesize that the HPV vaccine induces germinal center formation and propose to test this hypothesis by evaluating fine needle aspirates for the presence of GCTfh or GCB, which correlate with germinal center formation assessed by more comprehensive, albeit more invasive, methods (e.g., lymph node biopsy and immunohistology)^{23,24}. We also propose to measure HPV-specific GCB. In measuring GCB, we propose to assess the fraction of Bmem and PC precursors and how these numbers correlate with the magnitude and durability of Bmem responses and magnitude and durability of PC and antibody responses. We also propose to assess the gene expression profiles of single GCTfh and GCB cells to learn, for example, whether genes associated with B cell help (IL-21) or specific pattern recognition receptor pathways (TLR9) are upregulated in these cells. We also propose to examine the gene expression changes in blood activated by the first and second dose of this vaccine relative to baseline. These analyses will enable us to study associations between the innate immune activation and GC magnitude and between GCTfh or GCB gene expression profiles and the magnitude and durability of the antibody, PC, and Bmem responses. Moreover, these analyses will establish important benchmarks for future studies aimed at understanding the durability of immunity for candidate vaccines or natural infections (e.g., SARS-CoV-2).

In addition to understanding how effective vaccines work, a tremendous amount of resources is also being invested into the development of vaccines that maximize germinal centers to generate diverse B cell repertoires against highly variant pathogens (e.g., HIV and influenza). The general consensus from a very limited number of studies is that the Bmem repertoire is more diverse, lower affinity, and less somatically mutated than the plasma cell repertoire²⁵ and thus research efforts are in place to learn how to

Protocol Title: Assessing immunological basis of durable antibody responses to 9-valent HPV vaccination

diversify the PC repertoire, and thus serum Ab repertoire. We have shown that the 4-valent HPV vaccine elicits a highly diverse Bmem repertoire with relatively low somatic hypermutation (SHM) that still achieves high Ab affinity/neutralization potencies^{1,2}. The question remains whether the plasma cell repertoire induced by HPV vaccination has more SHM, higher affinity, and less diversity than the Bmem repertoire, as predicted? Given very new evidence that highly multi-valent antigens are less dependent on antigen affinity than antigen valency/avidity for generating GCB and PC²⁶, the HPV vaccine may not require as much affinity maturation to generate long-lived plasma cells and thus may generate equally diverse PC and serum Ab cell repertoires. This would be optimal and support the use of highly valent antigens in a variant pathogen vaccine design, but is untested. Thus, we propose to compare the diversity, SHM levels, gene expression profiles, and affinity of antigen-specific Bmem and PC repertoires using the HPV vaccine as a model.

4. Study Endpoints

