10. Frequency, function and phenotype of HPV-specific CD4 T cells at D0, D14, D30, D60, Visit 8 + 7±1 days, Visit 8 + 14±5 days, Visit 8 + 30±5 days, D180, Visit 13 + 7±1 days, Visit 13 + 14±5 days, Visit 13 + 30±5 days, D365, D730, D1095, D1460, D1825
11. HPV-specific L1 CD4 T cell epitopes
12. Titers of HPV-specific antibodies collected by microsampler at D0, D30, Visit 8 + 30±5 days, Visit 13 + 30±5 days, D365
13. Titers of binding and neutralizing HPV-specific antibodies and distribution of HPV-specific binding antibody isotypes (e.g., IgA, IgM, IgG) in serum at baseline (D0), D14, D30, D60, Visit 8 + 7±1 days, Visit 8 + 30±5 days, D180, Visit 13 + 7±1 days, Visit 13 + 30±5 days, D365, D730, D1095, D1460, D1825
14. Antibody epitopes of polyclonal antibodies in blood or monoclonal antibodies cloned from B cells at any study visit.

5. Study Intervention/Investigational Agent

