Protocol Title: Assessing immunological basis of durable antibody responses to 9-valent HPV vaccination

associated with tonic-clonic movements, the activity is usually transient and typically responds to restoring cerebral perfusion by maintaining a supine or Trendelenburg position.

The participant will be provided with a CDC vaccine information sheet (Refer to Appendix B).

At the end of the visit, the participant will also be instructed to promptly call 911 if signs of severe allergic reaction develop after leaving the clinic (hives, swelling of the face and throat, difficulty breathing, a fast heartbeat, dizziness, or weakness) or to call the clinic if he/she/they develop any unexpected or severe side effects from the vaccination. Participants calling the site will receive further instructions on the proper course of action, including a return to the clinic for immediate evaluation, if appropriate.

This visit will last approximately 60 minutes.

6.5 In person Follow-up Visits (D1 (optional visit), D7±1, D14±2, D30±5, Visit 8 +1 day (optional visit), Visit 8 + 7±1 days, Visit 8 + 14±5 days, Visit 8 + 30±5 days, Visit 13 + 7±1 days, Visit 13 + 14±5 days , Visit 13 + 30±5 days, D365±14, D730±14, D1095±14, D1460±14, D1825±30)

All participants will return for study-related blood draws (innate and adaptive assays) and saliva collection (antibody assays) post vaccination

- Study personnel will first review the participant's current health status and note any changes in health history since the screening visit, including current medication use and vaccination history.
- Blood for immunological assays will be drawn
- Saliva for antibody assays will be collected only on days indicated (D30±5, Visit 8 + 30±5 days, Visit 13 + 30±5 days, D365±14, D730±14)
- Optional procedure: Approximately 40 microliters of blood will be collected by finger prick and microsampler device on D30±5, Visit 8 + 30±5 days, Visit 13 + 30±5 days, and D365±5 (20 ul per device; Mitra Microsampler, Neoteryx, USA). This single-use, non-sterile device is intended to be used as a specimen collector of dried blood. It absorbs blood onto a cotton swab-like device, where the tip is covered in a hydrophilic porous material. It is non-cytotoxic, non-hemolytic, non-pyrogenic, and does not pose any sensitivity issues.

The visit will last approximately 30 minutes.

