17.4 How data and specimens will be handled

- 17.4.1 All de-identified samples will be stored at Emory Infectious Diseases Research Laboratory (EIDRL) at Hope Clinic by laboratory staff using only the study number, PTID, date of visit, and visit number, with the following exceptions: Dried blood samples collected by microsampler device and paired serum samples, as well as a serum aliquot from Visit 1 will be temporarily stored at EIDRL and then shipped to collaborators at Centers for Disease Control and Prevention using only a specimen ID, date of visit, and visit number. De-identified serum will be shipped to collaborators at EPFL using only a non-linked identifier and visit number. The data from immunological assays and gene expression analysis (RNA sequencing) will be linked to PTID, maintained by the laboratory, and accessible to investigators and laboratory staff. Laboratory data and demographic data may be linked by PTID for statistical analysis by investigators or collaborators (e.g., to control for age); however, PTID will not be published nor will the gene expression (RNA sequencing) data be linked to demographic data in order to protect participant privacy and prevent the discovery of participant identity.
- 17.4.2 Specimens and demographic data linked by PTID will be stored indefinitely, but all personal identifiable information (PII) and PII/PTID links will be destroyed once the laboratory analysis associated with this protocol is complete and the last manuscript associated with this protocol has been published.

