- 17.4.3 Study investigators and personnel will maintain the highest degree of confidentiality for the clinical and research information obtained from the participants. Medical and research records will be maintained in the strictest confidence. However, as a part of the quality assurance and legal responsibilities of a clinical study, investigators will permit authorized representatives of regulatory authorities to examine (and when required by applicable law, to copy) clinical records for the purpose of quality assurance reviews and evaluations of study safety and progress. Unless required by laws that permit copying of records, only the PTID associated with documents or with other participant data may be copied (and all personally identifying information will be removed). Authorized representatives described above are bound to maintain the strict confidentiality of medical and research information that is linked to identify individuals.
- 17.4.4 The blood tubes will be labeled at the Hope Clinic with a unique identifier and will be transported to the lab at the Hope Clinic in EHSO-approved transport containers. Fresh lymph node fine needle aspirate samples labeled with PTID and visit number performed at the Winship Cancer Institute or Hope Clinic will be transported to the Hope Clinic or [name] laboratory in a timely fashion in EHSO-approved transport containers. Fresh bone marrow aspirate samples labeled with PTID and visit number performed at the Winship site or Hope Clinic will be transported to the Hope Clinic

or [name] laboratory in a timely fashion in EHSO-approved transport containers. The dried blood microsamplers and paired serum samples, as well as serum samples from Visit 1 will be labeled at the Hope Clinic with a unique identifier and shipped to the collaborators at the Centers for Disease Control and Prevention. De-identified serum will be labeled with a unique identifier and shipped to collaborators at EPFL.

18. Provisions to Monitor the Data to Ensure the Safety of Participants

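### Aim 7 asks whether the microsampler can serve as an alternative to venous blood, but Objective 12 names only correlation with serum, which is blind to a constant fold bias

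*Protocol*

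**What the plan says.** Protocol Section 2 (Objectives, aim 7) sets the question: "To determine if a microsampler can be used an alternative to venous blood collection for measuring antibody responses in blood for surveillance programs".

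Protocol Section 1 (Study Summary, Exploratory Objective 12) says what would answer it: that vaccine-elicited antibody responses from the microsampler "correlate with antibody responses found in serum to demonstrate feasibility for surveillance programs". It names no other measure.

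Protocol Section 4.1.3, Exploratory Endpoint 12, is "Titers of HPV-specific antibodies collected by microsampler at D0, D30, Visit 8 + 30±5 days, Visit 13 + 30±5 days, D365". It lists titres and no comparison statistic. Section 17.1 describes the analysis as exploratory and descriptive.

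On the specimens, Section 6.4 says of the device: "This single-use, non-sterile device is intended to be used as a specimen collector of dried blood". Section 17.4.1 sends "Dried blood samples collected by microsampler device and paired serum samples" to the same outside laboratory, and Section 17.4.4 repeats this. The finger prick is optional (Sections 6.4 and 6.5), and the sample size is 16 (Section 1).

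**The concern.** Use as an alternative to a venous draw is a question about agreement: does the device give the same titre, or one that can be converted to it? Correlation asks only whether the two readings rise and fall together. The device collects dried blood and the comparator is serum, so a fold offset is possible, although nothing in the protocol shows that one exists.

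Absolute level matters here. Section 6.2.3 reads serostatus for binding antibodies against a laboratory cut-off, and a surveillance programme that applied such a cut-off to dried-blood titres would need to know the offset. For saliva, Aim 6 and Objective 8 put magnitude within the comparison with serum. The microsampler is the specimen proposed as an alternative to venous collection, yet its objective stops at correlation.

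**Working it through.** **1. No figure to reproduce.** The protocol states no sample size rationale, threshold or margin for this objective.

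**2. The algebra (no assumed titres needed).** Let device titre = k × serum titre × error. Then log(device) = log(k) + log(serum) + log(error). The constant log(k) drops out of both the covariance and the variances, so Pearson r on log titre is the same for every k > 0. Pearson r on raw titre and Spearman's rho are also unchanged.

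**3. Numerical confirmation (all inputs assumed).** The set-up was 16 people × 5 visits = 80 pairs; log10 serum means 0.3, 1.8, 2.3, 3.0, 2.4; between-person SD 0.4; device error SD 0.15; 2,000 runs with the same random draws for each bias.

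| Under-reading | Pearson r (log) | Spearman | Geometric mean ratio |
|---|---|---|---|
| none | 0.989 | 0.980 | 1.00 |
| 2-fold | 0.989 | 0.980 | 0.50 |
| 4-fold | 0.989 | 0.980 | 0.25 |
| 10-fold | 0.989 | 0.980 | 0.10 |

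The correlations do not move; the ratio recovers the bias.

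**4. With a detection floor.** Participants are seronegative at entry, so D0 readings may sit at the floor and the invariance is no longer exact when D0 is included. A second assumed set used person SD 0.3, serum error SD 0.1, device error SD 0.3, a floor of 0.5 log10, and two sets of visit means (wide 0, 2, 2.5, 3.5, 2.8; narrow 0, 1.5, 1.8, 2.5, 2.0).
- Five-visit r for 1-, 2- and 4-fold bias is 0.96, 0.96, 0.94 (wide) or 0.93, 0.91, 0.87 (narrow).
- An unbiased but noisier device (error SD 0.5) gives 0.91 (wide) or 0.83 (narrow), lower than the 4-fold-biased device.

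A reduced r therefore neither identifies bias nor sizes it.

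**5. Precision of the ratio on post-vaccination pairs.** There are four such visits (D30, Visit 8 + 30, Visit 13 + 30, D365). Keep device error SD 0.3 and serum error SD 0.1, average each person's four log10 differences, and use t on n − 1 degrees of freedom.

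*Device error independent at each visit.* The variance of a person's mean difference is (0.09 + 0.01)/4 = 0.025, so SD 0.158.
- n = 16: half-width 2.131 × 0.158/√16 = 0.084, so ×/÷ 1.21. An unbiased device gives 0.82 to 1.21; a 2-fold-low device 0.41 to 0.61.
- n = 8: half-width 2.365 × 0.158/√8 = 0.132, so ×/÷ 1.36. An unbiased device gives 0.74 to 1.36; a 2-fold-low device 0.37 to 0.68.

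*Half the device variance at person level (also assumed).* The variance is 0.045 + 0.045/4 + 0.01/4 = 0.0588, so SD 0.242.
- n = 16: half-width 0.129. Unbiased 0.74 to 1.35; 2-fold low 0.37 to 0.67. The two remain apart.
- n = 8: half-width 0.203. Unbiased 0.63 to 1.59; 2-fold low 0.31 to 0.80. The two overlap between 0.63 and 0.80.

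**6. Limits of agreement for an unbiased device.** With error SD 0.3: ±1.96 × √(0.09 + 0.01) = ±0.62 log10, a ratio of about 0.24 to 4.2. With SD 0.5: ±1.96 × √(0.25 + 0.01) = ±1.00, about 0.10 to 10. These are wide, and they will be estimated imprecisely.

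**The case against.** The strongest reply is that Objective 12 is one sentence in a summary table, not an analysis specification. Endpoint 12 is defined as titres. Where this protocol wants correlation as the endpoint it says so, as in Exploratory Endpoints 2a, 2c, 3a, 3c and 9. The statistic for an exploratory comparison is commonly left to the statistical analysis plan, which is not shown. Feasibility is also a lower bar than interchangeability: poor correlation is something calibration cannot repair, while a stable offset can be calibrated, so correlation is a defensible first test in a small volunteer group.

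Much of this stands. A reader might infer that the protocol locks in a wrong analysis. It does not, because Endpoint 12 leaves the comparison open and nothing prevents a ratio or agreement analysis. A reader might infer that the device is biased. The protocol gives no titres, device error or sign of bias. A reader might infer that the serum side is missing. It is not: Endpoint 13 lists serum titres at all five microsampler visits, and paired serum travels with the dried blood. A reader might also take the intervals above as a forecast, but every input beyond the algebra is assumed.

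What the reply does not answer is the gap between the two statements. The protocol itself says what would demonstrate feasibility, and that is narrower than Aim 7. An analysis plan could add agreement, yet a result that met Objective 12 as written could still be reported as the demonstration with the offset unknown.

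**Conclusion.** The point holds as a mismatch between an aim and the measure named for it. It is minor and worth correcting. The invariance of log-scale correlation to a constant fold shift is exact above the detection limit and rests on no assumed value. The simulated and computed magnitudes are illustrative only.

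The paired ratio would reveal an offset that correlation hides. On the assumed inputs, 16 people separate a 2-fold bias from none even with a sizeable person-level device effect. With about 8 people the intervals overlap, so separation may fail; it is not certain to, since the 2-fold-low interval there still lies below 1. Because the finger prick is optional, the number of pairs may well be below 16 per visit. The consequence is confined to one exploratory objective.

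**What to change.** Reword Objective 12 so that microsampler responses *correlate and agree with* the antibody responses found in serum. Then specify:

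- **Comparator:** the paired serum shipped with the dried blood (Sections 17.4.1 and 17.4.4), tested in the same laboratory with the same assay, separately for each HPV type. Endpoint 13 names no laboratory, and other serum goes to a different collaborator, so using its titres by default could mix laboratory and device effects.
- **Agreement:** for D30, Visit 8 + 30, Visit 13 + 30 and D365, the geometric mean ratio (microsampler/serum) with 95% confidence interval and the 95% limits of agreement on log titre, allowing for repeated pairs and a person-level device effect.
- **Serostatus:** seropositive/seronegative concordance at all five visits, including D0.
- **Correlation:** kept as descriptive.
- **Reading:** a stable offset is reported as a calibration factor, not a failure.

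The cost is one reworded exploratory objective and a little more analysis, with no new samples or visits. The downside is imprecision with at most 16 volunteers and an optional procedure, which the report should state.
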